Among 74 subjects with HCV GT2 infection in Part 1 of Study M14-868, no subject has experienced on treatment virologic failure or post-treatment relapse. Excluding one subject who was lost to follow-up, all 73 subjects with HCV GT2 infection achieved SVR₁₂. The SVR₁₂ rates for each of the treatment regimens were 96% (24/25) (including a subject who was lost to follow-up) of subjects treated with ABT-493 300 mg QD + ABT-530 120 mg QD for 12 weeks, 100% (24/24) of subjects treated with ABT-493 200 mg QD + ABT-530 120 mg QD for 12 weeks and 100% (25/25) of subjects treated with ABT-493 200 mg QD + ABT-530 120 mg QD + RBV for 12 weeks.

One hundred twenty-one (121) subjects with HCV GT3 infection were treated in Part 1 of Study M14-868. Among all subjects receiving the regimen tested in this study, i.e., ABT-493 300 mg and ABT-530 120 mg without RBV for 12 weeks, 93% (28/30 subjects) achieved SVR₁₂. One subject in this arm had no data available (HCV RNA < LLOQ at most recent visit) through Post-Treatment Week 12 and was counted as an SVR₁₂ non-responder. One subject in this arm experienced relapse at Post-Treatment Week 4.

In Study M14-868 Part 2, among 29 treatment-naïve non-cirrhotic subjects with GT3 infection treated for 8 weeks with ABT-493 300 mg QD + ABT-530 120 mg QD, no subject experienced on-treatment virologic failure or post-treatment relapse. One of the 29 subjects had missing SVR₁₂ data. Among 24 treatment-naïve cirrhotic subjects with

GT3 infection treated for 12 weeks with ABT-493 300 mg QD + ABT-530 120 mg QD, no subject experienced on-treatment virologic failure or post-treatment relapse.

In Study M14-868 Part 3, GT3-infected subjects with treatment experience and/or cirrhosis were treated with ABT-493/ABT-530 300 mg/120 mg QD for 12 and/or 16 weeks. Treatment-naïve GT3-infected subjects with cirrhosis achieved a SVR₁₂ rate of 98% (39/40) and treatment-experienced subjects with cirrhosis achieved a SVR₁₂ rate of 96% (45/47) following 12 and 16 weeks of treatment with ABT-493/ABT-530 300 mg/120 mg QD, respectively, with no virologic failures among treatment-naïve subjects with cirrhosis. The relapse rate among treatment-experienced subjects with cirrhosis following 16 weeks of treatment was 2% (1/46). Among treatment-experienced subjects without cirrhosis, the SVR₁₂ rates for the 12-week and 16-week regimens were 91% (20/22) and 96% (21/22), respectively.

To date, safety data across all Part 1 arms in Studies M14-867 and M14-868 encompassing 274 subjects treated with ABT-493 at doses 200 and 300 mg and ABT-530 at doses 40 and 120 mg (with and without RBV in Study M14-868) for 12 weeks show that the most frequently reported adverse events were fatigue, nausea, and headache (occurring in > 5% of subjects). Most of them were Grade 1 or 2 in severity. There were no increases in the frequency or severity of any adverse event between the different regimens of ABT-493 200 mg plus 40 mg or 120 mg ABT-530, and ABT-493 300 mg plus 120 mg ABT-530.

Of the 274 subjects, there have been 4 (1.5%) treatment-emergent SAEs reported combined (all assessed as not related to ABT-493 or ABT-530): pneumonia, atrial fibrillation, B-cell lymphoma, and metastatic prostate cancer. Two subjects (0.7%; 2/274) had treatment-emergent adverse events leading to treatment discontinuation. Both were GT3-infected subjects (ABT-493/ABT-530 [200 mg/120 mg] QD + RBV) of Study M14-868. One subject with history of irritable bowel disease discontinued for Grade 2 AE of abdominal pain assessed as having a reasonable possibility of relatedness to both the DAAs and RBV. Baseline alanine aminotransferase (ALT) elevations for this subject normalized during treatment and there were no on-treatment ALT elevations

above baseline; subject had total bilirubin elevations that were primarily indirect. The abdominal pain for this subject resolved after discontinuation from study drugs. The other subject discontinued for the aforementioned Grade 4 SAE of B-cell lymphoma for the purposes of initiating chemotherapy.

In both Studies M14-867 and M14-868, in all subjects with baseline ALT elevations, the ALT levels showed a trend toward normal or became normal with DAA treatment, and there have been no on-treatment ALT elevations above baseline. The ALT normalization pattern was similar across all arms (i.e., both ABT-493 and ABT-530 dose levels) in both studies. Other laboratory abnormalities were infrequent and were primarily associated with the well-described hemolytic effect of RBV, manifesting as Grade 1 anemia in total of 4 subjects, all occurring in Study M14-868 RBV-containing arms. Observed total bilirubin elevations were Grade 1 or 2 with predominantly indirect fraction, were mostly isolated occurrences, and normalized or stabilized with continued DAA therapy. Total bilirubin elevations were primarily observed in the RBV-containing arms.

The safety of the combination regimen of ABT-493 and ABT-530 in subjects with compensated cirrhosis is investigated in Study M14-867 Part 2 (ABT-493/ABT-530 [200 mg/120 mg] QD for 12 weeks) and Study M14-868 Part 2 (ABT-493/ABT-530 [300 mg/120 mg] QD for 12 weeks with and without ribavirin or for 16 weeks without ribavirin). Based on 82 subjects with compensated cirrhosis enrolled in these arms who have received 4 weeks or more of treatment, the ABT-493 and ABT-530 regimen has demonstrated a favorable safety profile in this patient population. The majority of adverse events have been Grade 1 or 2 and there have been no treatment discontinuations.

A detailed discussion of the preclinical pharmacology and toxicology, in vitro virology and metabolism, and clinical data for ABT-493, ABT-530 and the combination of ABT-493 and ABT-530 can be found in the ABT-493 and ABT-530 Fixed-Dose Combination Investigator's Brochure.

AbbVie evaluated the combination of ABT-493 (300 mg QD) + ABT-530 (120 mg QD) in healthy Western subjects in Phase 1 drug-drug interaction (DDI) studies and in Han

Chinese, Japanese and Caucasians in Study M15-432. Based on cross-study comparison, the exposures (C_{max} and AUC_{24}) in Japanese and Han Chinese subjects were comparable to the exposures observed in Western subjects. Overall, results from these studies demonstrate similar pharmacokinetic profiles between Han Chinese and Caucasian subjects and support parallel approach in the proposed China development strategy utilizing the Global Phase 3 dose.

AbbVie's IFN-free combination regimen of ABT-493 and ABT-530 provides a compelling opportunity for improving the treatment of HCV-infected patients in China and meeting significant unmet medical needs of these patients. The proposed regimen provides for an all oral, IFN-free treatment that is simpler, safer, shorter and more efficacious than currently available injection-based regimens for the treatment of HCV GT1 – 6.

Antiretroviral Therapy (ART) Drug-Drug Interaction Studies with ABT-493 and ABT-530

Phase 1 DDI studies of the ABT-493 + ABT-530 combination with HIV antiretroviral (ARV) drugs have been conducted in healthy volunteers and/or HIV-1 infected subjects.

The ABT-493 + ABT-530 combination had no clinically meaningful impact on the exposures ($\leq 80\%$) of evaluated ARV regimens: rilpivirine, raltegravir, dolutegravir, abacavir, lamivudine, ritonavir-boosted protease inhibitors (darunavir, lopinavir), elvitegravir, emtricitabine and tenofovir disoproxil fumarate (TDF).

Based on Phase 1 DDI studies, the exposures of ABT-493 and ABT-530 were not affected by rilpivirine and raltegravir.

Dolutegravir, lamivudine and abacavir (Triumeq[®]) coadministered with ABT-493 + ABT-530 was evaluated in a DDI study (Study M15-584 Arm 2). Coadministration was safe and well tolerated with mild adverse events reported. The exposures of dolutegravir, lamivudine and abacavir were similar with and without coadministration with ABT-493

and ABT-530 ($\leq 13\%$ difference). ABT-493 and ABT-530 exposures were slightly lower (25% to 28%) when administered with dolutegravir, lamivudine and abacavir.

ABT-493 is a substrate of an organic anion transporting polypeptide (OATP), therefore OATP inhibitors may increase the exposures of ABT-493. When ABT-493 + ABT-530 was administered with cyclosporine (400 mg), an OATP inhibitor, ABT-493 exposure increased to 5.1-fold to that of DAAs administered alone. The observed increase in exposure, however, was not associated with clinically significant safety findings.

Protease inhibitors as a class have potential to inhibit OATP, thus the larger exposure increases in ABT-493 with ritonavir boosted protease inhibitors than with ritonavir alone may result from interaction of ABT-493 with both the protease inhibitor and ritonavir components. Cobicistat has been shown in vitro and in vivo to have similar cytochrome P-450 enzyme and transporter inhibition potential as ritonavir.

When ABT-493 was administered with ritonavir, exposure of ABT-493 was 2-fold of ABT-493 exposure alone. Coadministration of ABT-493 + ABT-530 with ritonavir boosted protease inhibitors, darunavir QD or lopinavir BID, increased ABT-493 exposures, AUC and C_{max} , to 3- to 5-fold and 2.6 to 4.4-fold, respectively, while exposures of ABT-530 were similar with and without darunavir QD ($\leq 16\%$ change) and increased to 1.4 to 2.5-fold with lopinavir BID. The exposures of lopinavir ($\leq 24\%$ increase) or darunavir ($< 30\%$ increase) were comparable with and without DAA coadministration. Both the regimens (darunavir QD or lopinavir BID) tested were well tolerated with mild adverse events. Therefore, coadministration of ritonavir-boosted PIs is not recommended with ABT-493/ABT-530. Coadministration of ABT-493 + ABT-530 with ritonavir boosted atazanavir was studied in a DDI study that was terminated early due to an increase in ABT-493 exposure up to 16-fold and ABT-530 exposure up to 3-fold with Grade 1 and 2 increases in ALT and Grade 2 to 3 increase in total bilirubin (predominately indirect). Therefore, coadministration of atazanavir is contraindicated with ABT-493/ABT-530.

The combination of ABT-493 +ABT-530 was evaluated with Genvoya[®] (elvitegravir 150 mg, cobicistat 150 mg, emtricitabine 200 mg, tenofovir alafenamide 10 mg QD). Coadministration was safe and well tolerated, with mild adverse events reported and one grade 3 neutropenia deemed related to the combination of Genvoya[®], ABT-493 and ABT-530 in a black male subject with a low baseline ANC, leading to premature study drug discontinuation. The ABT-493 exposure increased to 3-fold and the ABT-530 exposure increased by 57%, with clinically insignificant increases in elvitegravir, cobicistat, tenofovir and emtricitabine exposures. Thus, cobicistat boosted elvitegravir will be allowed with ABT-493/ABT-530.

Efavirenz induces P-gp and exposures of ABT-493 and ABT-530 in the presence of efavirenz were approximately 3- and 2-fold lower, respectively, and thus coadministration of efavirenz and efavirenz-containing regimens is not recommended with ABT-493/ABT-530.

In summary, coadministration of HIV-PIs alone, ritonavir-boosted PIs and efavirenz is not recommended with ABT-493/ABT-530. Based on the above information, cobicistat-boosted elvitegravir, dolutegravir, abacavir, lamivudine, rilpivirine and raltegravir are allowed.

For a more detailed discussion of drug-drug interaction studies please refer to the ABT-493 and ABT-530 Fixed-Dose Combination Investigator's Brochures.³⁷

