5.2.2 Exclusion Criteria

A subject will not be eligible for study participation if he/she meets any of the following criteria:

1. Female subject who is pregnant, breastfeeding or is considering becoming pregnant during the study or for approximately 30 days after the last dose of study drug.
2. Recent (within 6 months prior to study drug administration) history of drug or alcohol abuse that could preclude adherence to the protocol in the opinion of the investigator.
3. Positive test result at Screening for hepatitis B surface antigen (HBsAg) or hepatitis B virus (HBV) DNA > LLOQ if HBsAg is negative.
4. HCV genotype performed during screening indicating co-infection with more than one HCV genotype.
5. Requirement for and inability to safely discontinue contraindicated medications or supplements listed in [Table 1](#) at least 2 weeks or 10 half-lives (whichever is longer) prior to the first dose of any study drug.
6. Clinically significant abnormalities, other than HCV infection or HCV/HIV co-infection, based upon the results of a medical history, physical examination, vital signs, laboratory profile, and a 12-lead electrocardiogram (ECG) that make the subject an unsuitable candidate for this study in the opinion of the investigator, including, but not limited to:

- Uncontrolled diabetes as defined by a glycated hemoglobin (hemoglobin A1C) level > 8.5% at the Screening Visit.
 - Active or suspected malignancy or history of malignancy (other than basal cell skin cancer or cervical carcinoma in situ) in the past 5 years.
 - Uncontrolled cardiac, respiratory, gastrointestinal, hematologic, neurologic, psychiatric, or other medical disease or disorder, which is unrelated to the existing HCV infection.
7. Any cause of liver disease other than chronic HCV-infection, including but not limited to the following:
- Hemochromatosis
 - Alpha-1 antitrypsin deficiency
 - Wilson's disease
 - Autoimmune hepatitis
 - Alcoholic liver disease
 - Steatohepatitis on liver biopsy considered to be the primary cause of the liver disease rather than concomitant/incidental with HCV infection
8. Screening laboratory analyses showing any of the following abnormal laboratory results:
- ALT > 10 × upper limit of normal (ULN)
 - AST > 10 × ULN
 - Estimated Glomerular filtration rate adjusted for the Chinese population (eGFR) < 50 mL/min/1.73 m² as estimated by the MDRD method, modified for the Chinese population (C-MDRD), according to the following formula:

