$$\text{eGFR} = 175 \times (\text{Serum Creatinine})^{-1.234} \times (\text{Age})^{-0.179} \times (0.79 \text{ if Female})$$
 - Total bilirubin > 3.0 ULN
 - Albumin < 2.8 g/dL
 - International normalized ratio (INR) > 2.3, unless subject has known hemophilia or is on a stable anticoagulant regimen affecting INR
 - Hemoglobin < 11 g/dL for women; < 12 g/dL for men
 - Platelets < 60,000 cells per mm³

- Absolute neutrophil count (ANC) < 1000 cells/μL.
9. History of solid organ transplantation.
 10. Receipt of any investigational product within a time period equal to 10 half-lives of the product, if known, or a minimum of 6 weeks (whichever is longer) prior to study drug administration.
 11. Requirement for chronic use of systemic immunosuppressants, including but not limited to, corticosteroids (prednisone equivalent of > 10 mg/day for > 2 weeks), azathioprine, or monoclonal antibodies (e.g., infliximab).
 12. Chronic human immunodeficiency virus, type 2 (HIV-2) infection.
 13. Consideration by the investigator, for any reason, that the subject is an unsuitable candidate to receive ABT-493/ABT-530.
 14. History of severe, life-threatening or other significant sensitivity to any excipients of the study drugs.
 15. Patients who can't participate in study per local law.

Additional Exclusion Criteria for Subjects with HCV/HIV-1 Co-infection:

16. For subjects on stable ART, taking anti-retroviral agent(s) other than those permitted based on AbbVie approval.
17. Treatment for an AIDS-associated opportunistic infection (OI) ([Appendix D](#)) within 12 months of Screening or prophylaxis for an AIDS-associated opportunistic infection within 6 months of Screening.
18. Diagnosis of any clinical AIDS-defining event within 12 months prior to Screening. A list of these events may be found in [Appendix D](#).

Rationale for Exclusion Criteria

- | | |
|---------------------|--|
| 1, 6, 8, 9, 13 – 18 | In order to ensure safety of the subjects throughout the study |
| 2, 5, 10 – 12 | In order to avoid bias for the evaluation of efficacy and safety, including concomitant use of other medications |
| 3, 4, 7 | To exclude subjects with hepatitis B and liver diseases other than HCV |

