5.2.3.4 Prohibited Therapy

Subjects must be able to safely discontinue any prohibited medications or supplements listed in [Table 1](#) at least 2 weeks or 10 half-lives (whichever is longer) prior to the first dose of any study drug and not use these during the entire Treatment Period and for 30 days following discontinuation of study drugs.

Table 1. Prohibited Medications and Supplements

Medication or Supplement Name
Red yeast rice (monacolin K), St. John's Wort
Carbamazepine, phenytoin, pentobarbital, phenobarbital, primidone, rifabutin, rifampin
Atorvastatin, lovastatin, simvastatin*
Astemizole, cisapride, terfenadine
Efavirenz containing regimens

* Some HMG-CoA reductase inhibitors (including atorvastatin, lovastatin, or simvastatin) should not be taken with the study drugs. Subjects receiving these statins should either switch to pravastatin or rosuvastatin prior to the first dose of study drugs or may interrupt statin therapy throughout the treatment period and until 30 days after the last dose of study drug, based on the investigator's judgment. If switching to or continuing pravastatin or rosuvastatin, it is recommended to reduce the pravastatin dose by 50% or limit the rosuvastatin dose to 10 mg QD when taking with the study drugs.

Use of ethinyl estradiol containing oral contraceptives with ABT-493 and ABT-530 combination was associated with ALT increases in some healthy female subjects. Hormonal contraceptives (including oral, topical [including vaginal rings], injectable, or implantable varieties) containing ethinyl estradiol may not be used from 2 weeks prior to the first dose of ABT-493/ABT-530 until 30 days after the end of ABT-493/ABT-530 dosing. Progestin-only contraceptives, such as those containing norethindrone, desogestrel, or levonorgestrel, without ethinyl estradiol, may be used with ABT-493/ABT-530. Post-menopausal hormone replacement therapy, such as with esterified or conjugated estrogens, i.e., not containing ethinyl estradiol, may be used with ABT-493/ABT-530 at the discretion of the Investigator.

Anti-HCV medications other than those specified in the protocol will not be allowed anytime during the Treatment Period.

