5.4.1.2 Failure to Maintain HIV Virologic Suppression

HIV-1 RNA will be assessed at each scheduled study visit during the Treatment Period and Post-Treatment Period, as detailed in [Appendix C](#).

For HCV/HIV-1 Co-Infected Subjects on Stable ART

The criteria for failure to maintain HIV virologic suppression is as follows:

- HIV-1 RNA ≥ 200 copies/mL confirmed on 2 consecutive tests at least 2 weeks apart, in a subject compliant with their HIV ART therapy.

At the time a confirmatory HIV-1 RNA is drawn, a sample for HIV-1 genotypic resistance testing may also be obtained; this sample may be analyzed if the subject's repeat plasma HIV-1 RNA is ≥ 500 copies/mL. A subject should remain on HCV study drug treatment and his/her current ART regimen while the failure to maintain HIV virologic suppression is being confirmed. A confirmatory HIV-1 RNA and HIV-1 genotypic resistance blood draw can be done as an unscheduled visit. However, if this blood draw falls on the date of a scheduled study visit ([Appendix C](#)), only a single HIV-1 RNA and HIV-1 genotypic resistance blood draw needs to be performed at this visit.

Clinical management of failure to maintain HIV-1 virologic suppression during the study (Treatment Period and Post-Treatment Period) will be handled by the site investigator according to current HIV treatment guidelines and local standard of care.

If the investigator wishes to change the HIV-1 ART regimen for a subject, it must be discussed with the AbbVie TA MD prior to the change being made, unless the change is being made to address an immediate safety concern.

During the Treatment Period, subjects with confirmed failure to maintain HIV-1 RNA suppression should continue study drug treatment unless there is a requirement for prohibited concomitant medications (Section 5.2.3.2 and Section 5.2.3.4) to construct a new HIV ART regimen.

For HCV/HIV-1 Co-Infected Subjects Naïve to ART

Clinical management of ART-naïve co-infected subjects during the study (Treatment Period and Post-Treatment period) will be handled by the site investigator according to current HIV treatment guidelines and local standard of care. During the Treatment Period, if an investigator deems it necessary to initiate HIV-1 ART for a subject, continuation of study drug treatment must be discussed with the AbbVie TA MD prior to ART initiation.

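### Section 3.0 calls atazanavir contraindicated and other HIV protease inhibitors not recommended, but the rule for continuing study drug after an on-treatment ART change relies on sections that name no HIV protease inhibitor

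*Protocol*

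**What the plan says.** The Protocol deals with antiretrovirals in four places.

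- **Section 3.0, interaction studies.** For atazanavir the conclusion is that "coadministration of atazanavir is contraindicated with ABT-493/ABT-530". The closing summary adds that "coadministration of HIV-PIs alone, ritonavir-boosted PIs and efavirenz is not recommended with ABT-493/ABT-530", and then that "cobicistat-boosted elvitegravir, dolutegravir, abacavir, lamivudine, rilpivirine and raltegravir are allowed". No HIV PI is among the allowed agents.
- **Section 5.2.3.4, Table 1.** The only antiretroviral entry in the table of prohibited medications is "Efavirenz containing regimens". The text around the table names no HIV PI either. For co-infected subjects it refers the investigator to the labels of the ART products.
- **Eligibility.** Exclusion 5 concerns "Requirement for and inability to safely discontinue contraindicated medications or supplements listed in" Table 1. Separately, Inclusion 15 requires a qualifying ART regimen based on sponsor approval, and Exclusion 16 removes subjects on stable ART who are "taking anti-retroviral agent(s) other than those permitted based on AbbVie approval".
- **Sections 5.2.3.2 and 5.4.1.2, on treatment.** A change of ART must be discussed beforehand with the sponsor's medical director, unless it answers an immediate safety concern. After confirmed loss of HIV suppression, study drug should continue "unless there is a requirement for prohibited concomitant medications (Section 5.2.3.2 and Section 5.2.3.4) to construct a new HIV ART regimen". For ART-naïve subjects, continuing study drug must be discussed with the sponsor before ART is started, and no exception is given.

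**The concern.** The protocol reaches an interaction conclusion in its background section and then runs its on-treatment rule from a list that does not carry that conclusion. A site changing ART while the subject is on study drug would look to Table 1 to see whether the new agent is prohibited. For an HIV PI, Table 1 is silent. Section 5.4.1.2 can then be read as saying that study drug continues, including with the one antiretroviral that Section 3.0 calls contraindicated.

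What is at stake is the safety of the co-infected subjects, all of whom have cirrhosis, and the reliability of their exposure and liver-safety data. The overall efficacy estimate is not seriously at stake.

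**Working it through.** This is a check of text against text. The plan offers no figure to reproduce.

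**Step 1: status of each agent, side by side.**

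| Agent | Section 3.0 | Table 1 |
|---|---|---|
| Atazanavir | contraindicated | absent |
| HIV PIs alone, ritonavir-boosted PIs | not recommended | absent |
| Efavirenz | not recommended | listed as prohibited |

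Table 1 cannot be explained as a list of contraindicated antiretrovirals only, because it includes one called not recommended and omits the one called contraindicated. Nor can it be explained as a list of everything not recommended, because efavirenz and boosted PIs share that status in one sentence and only efavirenz was carried over.

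**Step 2: which rules depend on the table.**

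- Exclusion 5 is limited by its wording to drugs listed in Table 1, so by itself it does not reach HIV PIs. Inclusion 15 and Exclusion 16 do not use Table 1 and cover antiretrovirals at entry.
- The continuation rule in Section 5.4.1.2 cites two sections. Section 5.2.3.4 is Table 1 and its accompanying text. Section 5.2.3.2 has no list of prohibited agents. Its sponsor-approval wording is attached to the regimen held for at least 8 weeks before screening. For a later change it asks for discussion.
- ART initiation in naïve subjects has its own rule, with prior discussion in every case.

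The gap is therefore at an ART change during treatment. The safeguard there is discussion, not approval, and prior discussion falls away for an immediate safety concern.

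**Step 3: the protocol's own exposure figures.**

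- Boosted atazanavir: ABT-493 up to 16-fold and ABT-530 up to 3-fold, with Grade 1 and 2 ALT and Grade 2 to 3 bilirubin increases; study terminated early (Section 3.0).
- Boosted darunavir or lopinavir: ABT-493 AUC to 3- to 5-fold, with both regimens reported as well tolerated (Section 3.0).
- Cirrhosis: preliminary data at 200 mg once daily show ABT-493 exposure about 3-fold that of non-cirrhotic subjects (Section 5.6.4.1.1).
- ALT elevations of Grade 2 or above are anticipated only above an ABT-493 AUC put at 33 times the projected non-cirrhotic mean at 300 mg (Section 5.6.4.1.1).

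As a rough scale, assume that the cirrhosis and interaction factors multiply and that the 3-fold factor carries over to 300 mg. The protocol states neither.

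- Atazanavir at its upper figure: 3 × 16 = 48, above 33. Without the cirrhosis factor it is 16, below 33.
- Interaction factor needed to reach 33 with cirrhosis: 33 / 3 = 11.
- Darunavir or lopinavir: 3 × 3 = 9 to 3 × 5 = 15, below 33.

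The 16-fold figure is an upper value, and Section 3.0 does not say whether it refers to AUC. The atazanavir range of 16 to 48 shows only that the matter is more than editorial. It predicts nothing for an individual subject.

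**Step 4: reach.** The cap is 16 co-infected subjects of about 160, and 16 / 160 = 10%. One subject who became an SVR12 non-responder after such a switch would move the overall rate by 1 / 160 = 0.6 percentage points. In the co-infected subset at its cap, the shift would be 1 / 16 = 6.3 points.

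**The case against.** The strongest reply is that antiretrovirals are controlled by permission, so Table 1 never needed to list them. Much of this stands, and it rules out two stronger readings.

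- **That subjects on HIV PIs could enter.** A reader might infer this from the gap between Section 3.0 and Exclusion 5. The documents do not support it: Inclusion 15 and Exclusion 16 make entry on ART depend on sponsor approval whatever Table 1 says.
- **That starting ART is left to the site.** A reader might infer this too. It is not supported, because continuation of study drug must be discussed with the sponsor before ART initiation, without exception.

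For ART changes, the reply is that Section 5.4.1.2 also cites Section 5.2.3.2, so any regimen without sponsor approval might count as prohibited. That reading is possible, and the literal one is not the only one. But Section 5.2.3.2 does not say it, and the approved regimens are not set out as a governing list. The allowed agents in Section 3.0 come closest, as a conclusion in the background text.

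Other safeguards are real. Investigators must consider interactions of concomitant medications, subjects are expected to stay on one ART regimen, and Section 6.1.7.1 has rules for ALT increases. These lower the chance and the consequence of an error but do not resolve the conflict.

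It is also fair that not recommended is weaker than contraindicated, so leaving boosted PIs off a prohibited list need not be a contradiction in itself. The listing of efavirenz, which has the same status, weakens that defence, and it does not help with atazanavir.

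**Conclusion.** The inconsistency is real and confined to ART changes during treatment. Section 3.0 calls one antiretroviral contraindicated, while the continuation rule in Section 5.4.1.2 depends on sections that do not name it. The remaining safeguard is a discussion that need not come first when there is an immediate safety concern. Entry and ART initiation are separately guarded.

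The reach is small: at most 16 subjects, and Section 12.1 of the SAP anticipates fewer co-infected subjects than expected when the protocol was written. The unguarded path needs an on-treatment change, to an HIV PI, without prior discussion. SVR12 overall is hardly affected. The point still deserves correction because it concerns safety and a stated rule conflicts with the protocol's own interaction finding.

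The conclusion rests on reading Sections 5.2.3.2 and 5.2.3.4 as written, and on no approved-regimen list elsewhere in these documents governing ART changes. It does not depend on the multiplied exposure figures. It takes no view on which status is clinically right for any agent.

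**What to change.** Reconcile three places so that they give each antiretroviral the same status for ART changes on treatment: the interaction conclusions in Section 3.0, Table 1 (and with it Exclusion 5), and the continuation rule in Section 5.4.1.2. The sponsor should decide the status of each agent, use one set of terms for contraindicated, prohibited and not recommended, and say which list a site must consult when a change cannot wait for discussion. If the sponsor-approved regimens are meant to govern ART changes as well as entry, Section 5.2.3.2 should say so and point to where they are listed.

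The cost is an administrative change or a short amendment. It needs no additional subjects or procedures and no change to the analysis.
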